Once the dried spots arrive at Emory University, two will be processed for RNA extraction, followed by library preparation and whole genome RNA sequencing to measure a profile of 30,000 genes. Lab technicians will extract RNA from the dried blood spots (DBS) and prepare RNA sequencing (RNAseq) libraries. This process will occur in three steps: (1) RNA extraction and isolation, (2) RNAseq library preparation, and (3) Sequencing.

- 1. RNA extraction and isolation. The RNA will be quantified using Qubit (Thermo Fisher Scientific) and quality assessed by RNA bioanalyzer chips (Agilent). See attachment "NEB Protocol" for more details on RNA extraction and isolation.
- 2. RNAseq library preparation. The lab technicians will use the New England biolabs kits. First, they will remove ribosomal RNAs using ribosomal depletion kit (NEB#E6310) and then prepare the RNAseq library using the NEBNext® Ultra™ II Directional RNA Library Prep with Sample Purification Beads (NEB#E7765). The technicians will quantify the library using qubit and checking the quality HS DNA bioanalyzer chips (Agilent). See attachment "RNA Extraction and Isolation from HemaSpot" for more details on the RNAseq library preparation protocol.

V4 03.22.2024 Page 12 of 16

| HRP- 503BIO | TEMPLATE: UH Biomedical Protocol | | |
|----------------|----------------------------------|----------------|---------|
| Approved: | 09/2021 | Prior Version: | 08/2019 |

3. Sequencing. Once the RNAseq libraries are made, the lab technicians will sequence them using NextSeq 500/550 mid output kits – 150 cycles (Illumina).

Qualitative analysis plan

Interviews will take place via a HIPAA-compliant commercial tele-health platform (i.e., Zoom for Healthcare) and be recorded then transcribed by hand. The RA, who will not conduct any interviews, will proof transcripts against the original recordings for accuracy. The transcribed interviews will be imported into the qualitative software program NVivo for analysis. At least two individuals experienced in qualitative data analysis will perform a line-by-line review and coding of each transcript independently using a constant comparative method of qualitative data analysis (Hseih & Shannon, 2005). The initial coding will consist of reading the narrative text and highlighting words or phrases that capture the experience with music therapy. Text will be coded as themes as identified from the narratives and will be organized into meaningful categories and subcategories. In the final step, a table with categories and subcategories of data, along with definitions for each category, will be constructed consistent with study objectives. All data from the interviews that appear to be directly related to the study aims will be extracted.

Strategies to optimize validity will include reviewing the coding among all coders, refining the coding until there is agreement. Members of the research team will review findings for accuracy of generated themes, interpretations of the data, and conclusions.

Risks to Research Participants

The participant may not like the MARI intervention included in the study. In that event, participants may ask the MT-BC to stop the intervention and choose not to participate in the rest of the intervention. The probability of this event is low, however, as it has not occurred in any prior music therapy studies and its occurrence is rare in music therapy practice. It is possible that the participant may experience discomfort providing peripheral blood samples via finger prick. A breach in participants' privacy and confidentiality may occur as a result of participating in this research study.

Provisions to Protect the Privacy Interests of Research Participants

All attempts will be made to ensure participants' privacy. The referrals will come from the participant's medical team. The participant's name will only appear on the consent form and the linking log. The linking log that identifies the participant's study ID to identifiable data will be stored on a password-protected, encrypted computer or secure server. All data that is stored in REDCap will identify the participant by the number assigned to them at the beginning of the study. Informed consent will occur in a private clinical room or consult room out of the earshot of others to maintain privacy.

Only aggregate data will be presented or published and will be presented such that individuals cannot be identified. Only IRB-approved study personnel will have access to participant data. All study personnel will be required to be certified in the protection of human subjects throughout the study.

Identifiable information will not be reused or disclosed to any person or entity outside of University Hospitals other than those identified in the protocol, except as required by law, for authorized oversight of the research study, or as specifically approved for use in another study by the IRB.

Potential Benefit to Research Participants

V4 03.22.2024 Page 13 of 16

| HRP- 503BIO | TEMPLATE: UH Biomedical Protocol | | |
|----------------|----------------------------------|----------------|---------|
| Approved: | 09/2021 | Prior Version: | 08/2019 |

Although not guaranteed, there is the possibility that the MARI intervention may reduce pain, anxiety and stress after their surgery. Furthermore, future surgical patients may benefit from the knowledge gained from this study.

Withdrawal of Research Participants

The study doctor or the sponsor can withdraw participation of research participants at any time without their consent for the following reasons:

- If the patient is admitted to the ICU following surgery and remain admitted to the ICU on the day when study procedures would typically begin.
- If, after the first day participation, the participant's clinical condition deteriorates enough that they are transferred to the ICU.
- If it appears to be medically harmful to the subject;
- If the subject fails to follow directions for participating in the study;
- If it is discovered that the subject does not meet the study requirements;
- If the study is canceled; or
- For administrative reasons, including competitive enrollment the target number of subjects has entered the study.

Alternatives to Participation

Instead of participating in this research study, patients can continue to work with their care team to manage their pain.

Costs to Research Participants

There is no cost to participate in this study.

Research Participant Compensation

Participants who complete the semi-structured interview will receive a \$25 gift card.

Provisions to Monitor the Data to Ensure the Safety of Research Participants

The study PI will monitor the study to ensure data integrity and the safety of the participants. The study coordinator will review the data for discrepancies on a regular basis and will review the study records for compliance with IRB requirements. The study team will hold regular weekly meetings to review study progress and any issues that may come up regarding data integrity and completeness.

V4 03.22.2024 Page 14 of 16

| HRP- 503BIO | TEMPLATE: UH Biomedical Protocol | | |
|----------------|----------------------------------|----------------|---------|
| Approved: | 09/2021 | Prior Version: | 08/2019 |

References

- Bergh, O., & Silverman, M. J. (2018). Effects of Music Therapy in the Form of Patient-Preferred Live Music on Mood and Pain with Patients on a Solid Organ Transplant Unit: A Randomized Pilot Study. *Music Therapy Perspectives*, *36*(1), 129–130. https://doi.org/10.1093/mtp/mix027
- [name], M. K., Denninger, J. W., Huffman, J. C., Joseph, M. G., Niles, H., Chad-Friedman, E., Goldman, R., Buczynski-Kelley, B., Mahoney, B. A., Fricchione, G. L., Dusek, J. A., Benson, H., Zusman, R. M., & Libermann, T. A. (2018). Specific Transcriptome Changes Associated with Blood Pressure Reduction in Hypertensive Patients after Relaxation Response Training. *Journal of Alternative and Complementary Medicine*, *24*(5), 486–504. https://doi.org/10.1089/acm.2017.0053
- [name], M. K., Dusek, J. A., Chang, B. H., Joseph, M. G., Denninger, J. W., Fricchione, G. L., Benson, H., & Libermann, T. A. (2013). Relaxation Response Induces Temporal Transcriptome Changes in Energy Metabolism, Insulin Secretion and Inflammatory Pathways. *PLoS ONE*, 8(5). https://doi.org/10.1371/journal.pone.0062817

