then the RA will ask the participant if it is ok for the research team to return at another time to see if they meet study criteria and are willing and able to participate in study procedures. If the participant says yes, the RA will return at least 24 hours later and repeat the above steps. If applicable, the RA will return each day that the patient is admitted and study staff are available to repeat the above steps until either (1) the participant's eligibility is confirmed and study procedures begin, (2) the participant says that they are no longer interested in participating in the study at all, (3) the participant becomes ineligible for any other reason (e.g. they are admitted to the ICU, or (4) the participant is discharged. Participants who change their mind about participating (reason 2), become ineligible for another reason (3), or are discharged will be withdrawn from the study. They may still receive music therapy services during their hospitalization after this withdrawal, but these will occur within routine clinical music therapy practice and no data on those sessions will be collected for this study.

The result of both the check in(s) with the provider and with the participant will be documented in REDCap. Participants that continue to meet eligibility criteria on day 1 post-surgery or another day through discharge, and are not withdrawn from the study for the reasons noted above will be considered to have "Initiated study procedures" following enrollment.

V4 03.22.2024 Page 5 of 16

| HRP- 503BIO | TEMPLATE: UH Biomedical Protocol | | | | | |
|----------------|----------------------------------|----------------|---------|--|--|--|
| Approved: | 09/2021 | Prior Version: | 08/2019 | | | |

Sharing of Results with Research Participants

☑ Results will **not** be shared with research participants

☑ Results will **not** be shared with research participants' doctors

Study Design

We will conduct a single arm non-randomized trial to determine the feasibility and acceptability of: (1) a tailored music-assisted relaxation and imagery intervention; (2) biological sample collection; and (3) mobile device patient-reported outcome (MDPRO) collection among adults hospitalized for pancreatic surgery experiencing acute pain. See Attachment "MUSICPUPS_Schematic" for a graphic representation of the study design.

Study Procedures

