In anticipation of a dropout rate of 33% following admission to the hospital (i.e., participants either not ever meeting pain criteria or choosing not to participate), we decided on a sample size of 30 participants with a plan to complete study procedures among the first 20 participants meeting full eligibility criteria. We based our sample size of 20 and definition of feasibility on prior research examining the feasibility of biological sample collection with music therapy (Holochwost et al, 2020). We have no prior experience using the HemaSpot HF for sample collection nor with delivery of the MARI intervention to this population and plan to start with a small sample size in order to refine procedures for a larger study. We hypothesize a 75% feasibility threshold for complete live MARI intervention delivery, PRO collection, and biological sample collection. We would consider failure to be completing less than 15/20 MARI interventions, 15/20 complete sets of PROs at Time 0, Time 1, and Time 2, 80% of MDPRO measures over the duration of the participant's hospitalization, and 45/60 blood sample collections.

We will use descriptive statistics (e.g., counts, percentages, mean, standard deviation, and median) to summarize participants' demographics and clinical characteristics (obtained from EHR), as well as feasibility measures including rates of enrollment, attrition, intervention participation, MARI recording use, biological sample collection/viability, and PRO collection. We will determine the feasibility of biological sample viability by quantifying whether individual participants provided enough biological samples for eventual testing. No formal hypothesis tests (e.g., linear mixed effects models) will be conducted on changes in PRO data as this is a feasibility study.

Blood sample analysis plan

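### The failure rule joins four minimums with *and*, and does not say how MDPRO completion becomes a study-level result, so the same data can be judged a failure or not

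*Combined protocol and SAP*

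**What the plan says.** The rule is in the Data Analysis Plan of the combined protocol and SAP. The plan first sets a general level: "We hypothesize a 75% feasibility threshold for complete live MARI intervention delivery, PRO collection, and biological sample collection". The next sentence defines failure. It opens "We would consider failure to be completing less than 15/20 MARI interventions", continues with "15/20 complete sets of PROs at Time 0, Time 1, and Time 2", and ends "80% of MDPRO measures over the duration of the participant's hospitalization, and 45/60 blood sample collections". One *less than* governs all four minimums, and *and* joins them.

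Three items have counts (20, 20 and 60). The MDPRO item has only a percentage. Under Study Procedures, MDPRO prompts come three times a day from the day after the live session until discharge, so the number due depends on length of stay.

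The Objectives and Study Design sections number three things to be judged: the intervention, biological sample collection and MDPRO collection. Study Design introduces them with "We will conduct a single arm non-randomized trial to determine the feasibility and acceptability of". The paragraph after the failure sentence promises descriptive rates for each measure. It does not say how the four minimums combine or how MDPRO completion is aggregated.

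**The concern.** Feasibility is the purpose of this trial, and this sentence is its only decision rule. Two things are left open.

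- **How the items combine.** Failure could mean missing all four (the literal *and*), missing any one, or a separate finding for each component. The first does not serve the component-wise objectives: a trial that missed three of the four would still not be a failure.
- **What MDPRO completion is at study level.** The 80% could apply to all prompts pooled, to the mean of participants' own rates, or to a number of participants who must each reach 80%. Pooling gives long-stay patients more weight; the other two weight participants equally.

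If neither is fixed in advance, the reading can be chosen after the results are known.

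**Working it through.** **Plan's own figures.** The plan states "In anticipation of a dropout rate of 33% following admission to the hospital", and "we decided on a sample size of 30 participants with a plan to complete study procedures among the first 20 participants meeting full eligibility criteria". 20 / (1 − 0.33) = 29.85, rounded up to 30, which agrees. 15/20 = 45/60 = 0.75, which matches the general threshold. The figures are sound; the problem is in the wording of the rule.

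**Combination: one result, three readings.** Take 14/20 MARI, 18/20 PRO sets, 85% MDPRO and 55/60 blood samples. Only MARI is below its minimum.

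- All four must be missed: not a failure.
- Any one missed: failure.
- Per component: MARI not feasible, the other three feasible.

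**Combination: probabilities.** This uses the three counted items only. Assume a common true completion rate p, binomial counts and, to begin with, independence between items and between the 60 samples.

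At p = 0.75:

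- MARI, and likewise PRO sets: P(X ≤ 14 | n = 20) = 0.383
- Blood: P(X ≤ 44 | n = 60) = 0.431
- Any missed: 1 − 0.617² × 0.569 = 0.78
- All missed: 0.383² × 0.431 = 0.06

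The same calculation at other rates:

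| True rate p | Any of three missed | All three missed |
|---|---|---|
| 0.70 | 0.958 | 0.258 |
| 0.75 | 0.783 | 0.063 |
| 0.80 | 0.438 | 0.005 |
| 0.85 | 0.142 | <0.001 |
| 0.90 | 0.023 | ~0 |

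**Effect of correlation at p = 0.75.**

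- MARI and PRO sets succeed or fail together, blood independent: any missed = 1 − 0.617 × 0.569 = 0.65; all missed = 0.383 × 0.431 = 0.17.
- All three fully linked, so that each participant completes everything or nothing: since 3 × 15 = 45, the three cut-offs coincide, and any missed = all missed = 0.383.

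**MDPRO aggregation.** The data here are illustrative. Stays of 5 and 14 days of prompts are assumed, giving 5 × 3 = 15 and 14 × 3 = 42 prompts.

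(a) Sixteen participants complete 13 of 15 and four long-stay participants complete 24 of 42.

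- Pooled: (16 × 13 + 4 × 24) / (16 × 15 + 4 × 42) = 304/408 = 74.5%, below 80%.
- Mean of participant rates: (16 × 13/15 + 4 × 24/42) / 20 = 80.8%, above 80%.

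(b) Fourteen participants complete 15 of 15 and six complete 6 of 15.

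- Pooled: (14 × 15 + 6 × 6) / 300 = 246/300 = 82.0%, above 80%.
- Participants reaching 80%: 14/20. This would miss a 15/20 bar, but that bar is borrowed from the other items and is not in the plan for MDPRO.

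So the choice of summary can change the verdict in either direction.

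**The case against.** The strongest reply is that the literal reading is the least plausible one. Falling short of a list can also mean not completing the whole package, or missing a threshold set for each item. The numbered objectives, the 75% level set for named components and the separate descriptive rates all favour a component reading. This stands. A reader might infer that the plan defines failure as missing all four and so can hardly ever fail; the documents do not support that as the settled meaning. But the any-one and per-component readings also lead to different statements about the study, and neither is written.

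On MDPRO, a reader might infer that the criterion has no unit at all. That is too strong: the wording refers to a single participant's stay and so points to a within-participant rate. Only the step from there to a study result is missing. Nor is 75% beside 80% a contradiction, because the failure sentence lists the Time 0-2 PRO sets and the MDPRO measures as separate items.

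On size, the gap depends on the assumptions. MARI delivery, Time 0-2 PROs and blood sampling belong to one linked bedside sequence, so independence overstates the gap. Full linkage is only a bound, however: the Blood sample procedures section expects sampling problems of its own, such as discomfort, device malfunction or refusal.

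Finally, no stated action depends on the word failure, and the component rates will be reported, so readers could apply a rule of their own. That limits the harm. It does not supply the prespecified verdict that the sentence is there to give.

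**Conclusion.** The point holds as a defect of wording in the trial's only decision rule. The sentence does not settle how four minimums combine, its literal form does not serve the component objectives, and the MDPRO item lacks a study-level summary.

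The consequence is largest near the thresholds. At a true rate of 75%, any-missed against all-missed is 0.78 against 0.06 under independence, and 0.65 against 0.17 with MARI and PRO sets linked. There is no gap on these three items if they are fully linked. At a true rate of 90% the independence figure for any missed is 0.02, so the reading would seldom matter for these items. These probabilities rest on a common completion rate, binomial counts and independent samples within a participant. The MDPRO examples show that verdicts can conflict, not how often they will.

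A reader might also infer that the study should proceed only if all four components pass, or that MDPRO needs 75% of participants to reach 80%. Neither rule is in the documents; both are choices for the sponsor.

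**What to change.** Replace the failure sentence with a separate verdict for each component, at the cut-offs already in the plan. A component is not feasible if:

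- fewer than 15/20 live MARI sessions are completed;
- fewer than 15/20 complete Time 0-2 PRO sets are obtained;
- fewer than 45/60 blood samples are collected; or
- MDPRO completion is below 80%.

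Define MDPRO completion before data are seen. One option that fits the present wording is the mean across participants of prompts completed divided by prompts scheduled from Day 2 to discharge. State how prompts falling after withdrawal or ICU transfer count, since Withdrawal of Research Participants provides for both. Report the pooled rate as secondary.

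The cost is one paragraph of protocol text and no new data. The downside is that a missed component can no longer be offset by the others. At borderline rates at least one miss is likely (0.65 to 0.78 on the three counted items at a true 75%, unless all three are closely linked). Any overall progression rule, or a minimum number of participants reaching 80% of MDPRO prompts, is for the sponsor to decide and is not needed for this correction.

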All HemaSpot-HF will be prelabeled with a Study ID (e.g., 1,2,3,4, 5), the appropriate study time series (i.e., Time 0, Time 1, or Time 2), and a line for the research assistant to write the date and time the sample was collected.

When collecting the blood sample, the research assistant will follow Spot On Sciences' procedure which can be viewed here (https://www.youtube.com/watch?v=rm8 jfOwlus). These procedures are as follows:

- Put on a pair of protective gloves;
- 2) Clean and sanitize a tray table on which to place the HemaSpot materials;
- 3) Lay out the materials from the HemaSpot kit on a tray table in the participant's room;
- 4) Clean the participant's finger using an alcohol wipe;
- 5) Remove the cap from the lancet and position the end against the inside tip of the middle or ring finger;
- 6) Press the lancet firmly on the participant's finger until it activates with a click;
- 7) Wipe away the first drop of blood with a sterile gauze;
- 8) Position the lanced finger over the center of the HemaSpot;
- 9) Provide gentle pressure on the end of the finger, and let three drops of blood drip from the finger onto the center of the HemaSpot;
- 10) Wait one minute for the wicking process to complete;
- 11) Bandage the participant's finger;

V4 03.22.2024 Page **8** of **16**

| HRP- 503BIO | TEMPLATE: UH Biomedical Protocol | | | | | |
|----------------|----------------------------------|----------------|---------|--|--|--|
| Approved: | 09/2021 | Prior Version: | 08/2019 | | | |

12) Close the HemaSpot firmly ensuring that the latch is secure.

These steps will occur at Time 0, Time 1, and Time 2, with the RA sampling a different finger from the participant at each time. The RA will note any challenges to blood sample collection (e.g., participant discomfort, device malfunction, participant refusal) and record these in REDCap following the procedure.

Following blood sample collection, the RA will ensure that the samples are properly labeled and their collection are noted in REDCap. The three samples will be placed in a secure padded envelope and locked in the Connor Whole Health Research Office in Wearn 548 or in the DCRU lab in the Wearn building until they are shipped to the Emory lab for analysis via UPS.

Suicidal Ideation, Acute Anxiety and Adverse Event Mitigation Plan

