We are not collecting genetic data. We are not performing any genetic profiling. We are performing gene expression analysis, and this is different from genetic profiling. This is a pilot study to collect information in preparation for an appropriately powered study. To establish procedural elements, it is necessary to test procedures including the MARI intervention, peripheral blood sampling, and mobile device patient-reported outcome collection as these have not been utilized in prior studies with this population. We have already consulted with statisticians and based on our previous findings in music intervention, we need 87 pre- and post-measures on subjects for the fully powered study. After this pilot study, we intend to launch a multi-center feasibility study in collaboration with other institutions.

We will plan on conducting the following gene expression analyses as specified for all three-time points (Time 0, Time 1, and Time 2). The gene expression analysis will be performed at [name] Systems biomedicine lab at Emory University.

A large part of the human genome is transcribed into various forms of RNA, and the global gene expression profile (GEP) changes measure expression changes in genes over time due to an intervention.

Accordingly, our long-term goal of this line of research will be to examine whether pain intensity changes after the MARI intervention are associated with specific changes in gene expression profiles (GEP) and pathophysiologic pathways that correspond with the elicitation of the relaxation response ([name] et al., 2013, 2018; Dusek et al., 2008).

V4 03.22.2024 Page 11 of 16

| HRP- 503BIO | TEMPLATE: UH Biomedical Protocol | | |
|----------------|----------------------------------|----------------|---------|
| Approved: | 09/2021 | Prior Version: | 08/2019 |

Our prior work was conducted among healthy adults ([name] et al., 2013; Dusek et al., 2008) or hypertensive patients ([name] et al., 2018) living in the community using PaxGene tubes to collect whole blood. In the intervening years, the technology of dried blood spot (DBS) collection of samples has improved and has been used for GEP analysis.

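### The blood failure rule (45/60) pools single collections across three times, so a pass does not show that before-after samples can be obtained within participants

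*Combined protocol and SAP*

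**What the plan says.** The Data Analysis Plan enrols 30, with "a plan to complete study procedures among the first 20 participants meeting full eligibility criteria". It then states: "We hypothesize a 75% feasibility threshold for complete live MARI intervention delivery, PRO collection, and biological sample collection". The failure limits follow in one sentence. For PROs the limit is "15/20 complete sets of PROs at Time 0, Time 1, and Time 2", a count of participants. For blood and the mobile-device measures it is "80% of MDPRO measures over the duration of the participant's hospitalization, and 45/60 blood sample collections", where the blood part is a count of single samples.

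Sampling is serial within each participant. Blood sample procedures says: "These steps will occur at Time 0, Time 1, and Time 2, with the RA sampling a different finger from the participant at each time".

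On viability, the Data Analysis Plan adds that it will be judged by whether individual participants gave enough samples for later testing. It does not define enough, sets no cut-off, and leaves this assessment out of the failure sentence.

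The Blood sample analysis plan intends expression profiling at all three times and a comparison of baseline with post-intervention samples. It also says that a confident comparison across the three times is out of reach at this sample size and belongs to a later randomized trial. On the later programme it says: "we need 87 pre- and post-measures on subjects for the fully powered study".

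**The concern.** Before-after expression work compares a person with themselves, so its unit is the participant who has a baseline sample and at least one later one. A pooled count does not measure that. Fifteen losses can be concentrated in five people, which leaves fifteen full series. They can also be spread one each over fifteen people, which leaves five. Both give 45/60 and both pass.

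The PRO rule shows that the authors think in within-person sets when the same three times are involved, and no reason is given for using another unit for blood. At stake is the verdict on the second objective, the feasibility of biological sample collection. It could be declared met when many of the within-person samples that the programme is preparing for are absent, and nothing in the failure rule would reveal it.

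**Working it through.** **Inputs.** From the protocol: 20 participants, 3 samples each, a 75% threshold, 45/60 for blood, 15/20 for PRO sets, 33% dropout and 30 enrolled. Assumed: a per-prick success rate p, independent between pricks. The protocol gives no such rate, so a range is shown.

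**The plan's own figures.** 20 × 3 = 60 and 0.75 × 60 = 45. 20 / (1 − 0.33) = 29.9, rounded up to 30. Both reproduce.

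**Complete series at exactly 45/60.** Let c be the number of participants with all three samples. Anyone else gives at most two, so 3c + 2(20 − c) ≥ 45, hence c ≥ 5. Also 3c ≤ 45, hence c ≤ 15. Exact enumeration of the presence patterns confirms the range 5 to 15. If the 15 losses fall at random among the 60 samples, the expected number is 20 × C(57,15)/C(60,15) = 8.3. For a pooled count to guarantee 15 complete series it would have to be 3(15) + 2(5) = 55/60.

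**Before-after pairs (Time 0 plus at least one later sample) at exactly 45/60.**
- All 15 losses at Time 0: 5 + 20 + 20 = 45 samples and 5 pairs. This is the floor.
- All losses at Times 1 and 2: a pair breaks only if both later samples are lost, so 15 losses break at most 7 pairs and at least 13 remain.
- All 15 losses at Time 2: all 20 pairs remain, with only 5 complete series.
- Random losses: expected pairs are 20 × [C(57,15) + 2 × C(57,14)]/C(60,15) = 14.1.

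**Behaviour of the rules under independence.** The pair probability is p × (1 − (1 − p)²); at p = 0.80 it is 0.80 × 0.96 = 0.768. The complete-series probability is p³. The probabilities of passing are binomial tails. The column for both rules comes from exact enumeration of the joint distribution.

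| p | P(≥45/60) | Expected complete series | P(≥15 complete series) | Pair probability | P(≥15 pairs) | P(≥45/60 and ≥15 pairs) |
|---|---|---|---|---|---|---|
| 0.75 | 0.57 | 8.4 | 0.003 | 0.703 | 0.43 | 0.37 |
| 0.80 | 0.87 | 10.2 | 0.03 | 0.768 | 0.69 | 0.66 |
| 0.85 | 0.99 | 12.3 | 0.15 | 0.831 | 0.89 | 0.89 |
| 0.90 | >0.99 | 14.6 | 0.53 | 0.891 | 0.98 | 0.98 |

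At p = 0.80 the pooled rule usually passes while only about half the series are expected to be complete.

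**The case against.** Several points on the other side have force.

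- **Pairs are not triples.** A before-after comparison needs Time 0 and one later sample. If the losses are late, complete series can be few while pairs stay largely intact. This stands, and it is why the added criterion should be on pairs.
- **The extreme is unlikely.** Five pairs requires 15 people to fail at Time 0 and then all succeed twice. Nothing in the protocol suggests that pattern. This stands: 5/20 is a bound.
- **A per-collection rate is a reasonable unit for an unfamiliar device.** The team states that it has no experience with this collector, and the stated primary interest is collecting samples of sufficient quality. This supports keeping 45/60, but not relying on it alone.
- **The PRO rule gives some protection.** The same research assistant collects PROs and blood at the same visits, so 15/20 PRO sets limits loss of whole visits. It does not limit failed or refused pricks, which Blood sample procedures anticipates.
- **Participant-level viability is already planned.** It is, and the time-labelled records would show a shortfall. Without a definition or a pass mark, it cannot change the verdict.
- **The feasibility definition is attributed to an earlier study.** That study may justify a pooled count, but the protocol does not repeat the reasoning.

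A reader might also infer that the powered study must be scaled up by the 25% floor. The documents do not support that. The floor for complete series is not a yield of pairs. The protocol does not say that the 87 are blood pairs, or that 45/60 will serve as a planning yield, and it puts a multi-center feasibility study next. Even taking the 87 as pairs and assuming independent 75% success, the pair yield is 0.75 × (1 − 0.25²) = 70%. That means 87/0.703 = about 124 participants, against 87/0.75 = 116: a modest difference.

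**Conclusion.** The concern holds as a mismatch between the blood rule and the question that the pilot has to answer. A pass at 45/60 is compatible with 5 to 15 complete series out of 20 (about 8 under random loss) and with as few as 5 before-after pairs (about 14 under random loss). The ranges follow from counting alone. The random-loss figures assume that the 15 losses are unrelated to person or time, and the probabilities of passing assume independent pricks at a rate that the protocol does not give. Losses clustered in a few participants would leave more complete series.

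Two stronger readings should be resisted. One is that a pass is likely to hide only five usable participants; that is a worst case. The other is that blood should simply take the PRO form, 15/20 complete triples. Expecting 15 triples needs about 91% success per prick (0.75^(1/3) = 0.909), and at 80% the chance of meeting that bar is 3%. It would also declare failure with 20, 20 and 14 samples at the three times, although every before-after pair is present.

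The statement that comparison across the three times is out of reach limits inference in this study. It does not remove the need to learn whether paired samples can be collected.

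**What to change.** In the Data Analysis Plan, keep 45/60 as the collection-level limit and add a participant-level limit to the same failure sentence: fewer than 15/20 participants with a Time 0 blood sample plus at least one post-intervention sample. Use the same pairing to define what counts as enough samples in the viability statement. Report alongside, without a pass mark, the number of participants with all three samples and the number of collections at each time.

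The cost is a sentence or two. No new data are needed, because the collectors are prelabelled by time and each collection is noted in REDCap. The downside is a somewhat stricter rule: at an assumed independent 80% per prick, the paired limit alone is met about 69% of the time and both limits together about 66%, against 87% for 45/60 alone. At 90% per prick the added limit costs almost nothing (98% for both).
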